Appendix 15 Clinical Dementia Rating (CDR) [61]

This is a semi-structured interview. Please ask all of these questions. Ask any additional questions necessary to determine the subject's CDR. Please note information from the additional questions.

Memory Questions for Informant:

1. Does he/she have a problem with his/her memory or thinking?

 Yes	 No
------------------------------	-----------------------------

 - 1a. If yes, is this a consistent problem (as opposed to inconsistent)?

 Yes	 No
------------------------------	-----------------------------
2. Can he/she recall recent events?

 Yes	 No
------------------------------	-----------------------------
3. Can he/she remember a short list of items (shopping)?

 Usually	 Sometimes	 Rarely
----------------------------------	------------------------------------	---------------------------------
4. Has there been some decline in memory during the past year?

 Usually	 Sometimes	 Rarely
----------------------------------	------------------------------------	---------------------------------
5. Is his/her memory impaired to such a degree that it would have interfered with his/her activities of daily life a few years ago (or pre-retirement activities)? (collateral sources opinion)

 Yes	 No
------------------------------	-----------------------------
6. Does he/she completely forget a major event (e.g., trip, party, family wedding) within a few weeks of the event?

 Usually	 Sometimes	 Rarely
----------------------------------	------------------------------------	---------------------------------
7. Does he/she forget pertinent details of the major event?

 Usually	 Sometimes	 Rarely
----------------------------------	------------------------------------	---------------------------------
8. Does he/she completely forget important information of the distant past (e.g., birthdate, wedding date, and place of employment)?

 Usually	 Sometimes	 Rarely
----------------------------------	------------------------------------	---------------------------------
9. Tell me about some recent event in his/her life that he/she should remember. (For later testing, obtain details such as location of the event, time of day, participants, how long the event was, when it ended and how the subject or other participants got there).

Within 1 week:

Within 1 month:

10. When was he/she born? _____
11. Where was he/she born? _____
12. What was the last school he/she attended?

Name _____

Place _____

Grade _____
13. What was his/her main occupation/job (or spouse's job if subject was not employed)? _____
14. What was his/her last major job (or spouse's job if subject was not employed)? _____
15. When did he/she (or spouse) retire and why? _____

Orientation Questions for Informant:

How often does he/she know of the exact:

1. Date of the Month?

Usually Sometimes Rarely Don't know

2. Month?

Usually Sometimes Rarely Don't know

3. Year?

Usually Sometimes Rarely Don't know

4. Day of the Week?

Usually Sometimes Rarely Don't know

5. Does he/she have difficulty with time relationships (when events happened in relation to each other)?

Usually Sometimes Rarely Don't know

6. Can he/she find his/her way about familiar streets?

Usually Sometimes Rarely Don't know

7. How often does he/she know how to get from one place to another outside his/her neighborhood?

Usually Sometimes Rarely Don't know

8. How often can he/she find his/her way about indoors?

Usually Sometimes Rarely Don't know

Judgment and Problem Solving Questions for Informant:

1. In general, if you had to rate his/her abilities to solve problems at the present time, would you consider them: As good as they have ever been

Good, but not as good as before

Fair

Poor

No ability at all

2. Rate his/her ability to cope with small sums of money (e.g., make change, leave a small tip):

No loss

Some loss

Severe loss

3. Rate his/her ability to handle complicated financial or business transactions (e.g., balance check-book, pay bills):

No loss

Some loss

Severe loss

4. Can he/she handle a household emergency (e.g., plumbing leak, small fire)?

As well as before

Worse than before because of trouble thinking

Worse than before, another reason (why) _____

5. Can he/she understand situations or explanations?

Usually Sometimes Rarely Don't know

6. Does he/she behave* appropriately [i.e., in his/her usual (premorbid) manner] in social situations and interactions with other people?

Usually Sometimes Rarely Don't know

*This item rates behavior, not appearance.

Community Affairs Questions for Informant: Occupational

- 1. Is the subject still working? Yes No N/A
If not applicable, proceed to item 4
If yes, proceed to item 3
If no, proceed to item 2
- 2. Did memory or thinking problems contribute to the subject's decision to retire? (Question 4 is next) Yes No D/K
- 3. Does the subject have significant difficulty in his/her job because of problems with memory or thinking?
Rarely or Never Sometimes Usually Don't know

Social

- 4. Did he/she ever drive a car? Yes No
- 5. Does the subject drive a car now? Yes No
- 6. If no, is this because of memory or thinking problems? Yes No
- 7. If he/she is still driving, are there problems or risks because of poor thinking? Yes No
- 8. Is he/she able to independently shop for needs?
Rarely or Never Sometimes Usually Don't know
(Needs to be accompanied on any shopping trip) (Shops for limited number of items; buys duplicate items or forgets needed items)
- 9. Is he/she able to independently carry out activities outside the home?
Rarely or Never Sometimes Usually Don't know
(Generally unable to perform activities without help) (Limited and/or routine, e.g., superficial participation in church or meetings; trips to beauty parlor) (Meaningful participation in activities, e.g., voting)

10. Is he/she taken to social functions outside a family home? Yes No
If no, why not? _____

- 11. Would a casual observer of the subject's behavior think the subject was ill? Yes No
- 12. If in nursing home, does he/she participate well in social functions (thinking)? Yes No

IMPORTANT:

Is there enough information available to rate the subject's level of impairment in community affairs?

Yes No

If not, please probe further.

Community Affairs: Such as going to church, visiting with friends or family, political activities, professional organizations such as bar association, other professional groups, social clubs, service organizations, educational programs.

*Please add notes if needed to clarify subject's level of functioning in this area.

Home and Hobbies Questions for Informant:

1a. What changes have occurred in his/her abilities to perform household chores? _____

1b. What can he/she still do well? _____

2a. What changes have occurred in his/her abilities to perform hobbies? _____

2b. What can he/she still do well? _____

3. If in nursing home, what can he/she no longer do well (H and H)? _____

4. Everyday Activities (Blessed):

	 No loss	 severe	 loss
• Ability to perform household tasks	0	0.5	1

Please describe: _____

5 Is he/she able to perform household chores at the level of: (Pick one Informant does not need to be asked directly).

No meaningful function.
(Performs simple activities, such as making a bed, only with much supervision)

Functions in limited activities only.
(With some supervision, washes dishes with acceptable cleanliness; sets table)

Functions independently in some activities.
(Operates appliances, such as a vacuum cleaner; prepares simple meals)

Functions in usual activities but not at usual level.

Normal function in usual activities.

IMPORTANT:

Is there enough information available to rate the subject's level of impairment in HOME & HOBBIES?

Yes No

If not, please probe further.

Homemaking Tasks: Such as cooking, laundry, cleaning, grocery shopping, taking out garbage, yard work, simple care maintenance, and basic home repair.

Hobbies: Sewing, painting, handicrafts, reading, entertaining, photography, gardening, going to theater or symphony, woodworking, participation in sports.

Personal Care Questions for Informant:

*What is your estimate of his/her mental ability in the following areas?

*A box-score of 1 can be considered if the subject's personal care is impaired from a previous level, even if they do not receive prompting.

A. Dressing (Blessed)	Unaided	Occasionally misplaced buttons, etc.	Wrong sequence commonly forgotten items	Unable to dress
	0	1	2	3
B. Washing, grooming	Unaided	Needs Prompting	Sometimes needs help	Always or nearly always needs
	0	1	2	3
C. Eating habits	Cleanly proper utensils	Messily; spoon	Simple solids	Has to be fed completely
	0	1	2	3
D. Sphincter control (Blessed)	Normal complete control	Occasionally wets bed	Frequently wets bed	Doubly incontinent
	0	1	2	3

Memory Questions for Subject:

1. Do you have problems with memory or thinking? Yes No

2. A few moments ago your (spouse, etc.) told me a few recent experiences you had. Will you tell me something about those? (Prompt for details, if needed such as location of the event, time of day, participants, how long the event was, when it ended and how the subject or other participants got there).

Within 1 week

_____ 1.0 – Largely correct
 _____ 0.5 – Partly correct
 _____ 0.0 – Largely incorrect

Within 1 month

_____ 1.0 – Largely correct
 _____ 0.5 – Partly correct
 _____ 0.0 – Largely incorrect

3. I will give you a name and address to remember for a few minutes. Repeat this name and address after me: (Repeat until the phrase is correctly repeated or to a maximum of three trials).

Elements	1	2	3	4	5
	John	Brown,	42	Market Street,	Chicago
	John	Brown,	42	Market Street,	Chicago
	John	Brown,	42	Market Street,	Chicago

(Underline elements repeated correctly in each trial).

4. When were you born?

5. Where were you born?

6. What was the last school you attended?

Name _____

Place _____

Grade _____

7. What was your main occupation job (or spouse if not employed)? _____

8. What was your last major job (or spouse if not employed)?

9. When did you (or spouse) retire and why?

10. Repeat the name and address I asked you to remember:

Elements	1	2	3	4	5
	John	Brown,	42	Market Street,	Chicago

(Underline elements repeated correctly).

Orientation Questions for Subject:

Record the subject's answer verbatim for each question

1. What is the date today? Correct Incorrect

2. What day of the week is it? Correct Incorrect

3. What is the month? Correct Incorrect

4. What is the year? Correct Incorrect

5. What is the name of this place? Correct Incorrect

6. What town or city are we in? Correct Incorrect

7. What time is it? Correct Incorrect

8. Does the subject know who the informant is (in your judgment)? Correct Incorrect

Judgment and Problem-Solving Questions for Subject:

Instructions: If initial response by subject does not merit a grade 0, press the matter to identify the subject's best understanding of the problem. Circle nearest response.

Similarities:

Example: "How are a pencil and pen alike? (Writing instruments) How are these things alike?" Subject's Response

1. turnip.....cauliflower_____
 (0 = vegetables)
 (1 = edible foods, living things, can be cooked, etc.)
 (2 = answers not pertinent; differences; buy them)
2. desk.....bookcase
 (0 = furniture, office furniture; both hold books)
 (1 = wooden, legs)
 (2 = not pertinent, differences)

Differences:

Example: "What is the difference between sugar and vinegar? (sweet vs sour) What is the difference between these things?"

3. lie.....mistake_____
 (0 = one deliberate, one unintentional)
 (1 = one bad the other good – or explains only one)
 (2 = anything else, similarities)
4. river.....canal_____
 (0 = natural - artificial)
 (2 = anything else)

Calculations:

5. How many nickels in a dollar? Correct Incorrect
6. How many quarters in \$6.75? Correct Incorrect
7. Subtract 3 from 20 and keep subtracting 3 from each new number all the way down. Correct Incorrect

Judgment:

8. Upon arriving in a strange city, how would you locate a friend that you wished to see?
 (0 = try the telephone book, go to the courthouse for a directory; call a mutual friend)
 (1 = call the police, call operator (usually will not give address))
 (2 = no clear response)
9. Subject's assessment of disability and station in life and understanding of why he/she is present at the examination (may have covered, but rate here):
 Good Insight Partial Insight Little Insight

Global CDR

Use all the information you get to make the most appropriate judgment. Evaluate the six functional domains separately, fill in the scores in the corresponding “_”, and note that the scores are scored only when the decline in ability is caused by cognitive impairment. If the severity of the dysfunction is between two levels, it is assessed in principle at a severe level. Finally, the scores of the six functional domains are combined and the CDR overall score (global CDR) is summarized according to the following principles:

1. Memory (M) is the main item and the other 5 items are secondary items;
2. When $M=0.5$, $CDR \neq 0$, can only be $=0.5$ or 1 ;
3. $CDR=M$ (memory score):
 - 1) When at least 3 secondary items are the same as the memory score;
 - 2) When there are only 1 or 2 minor item scores = M, no more than 2 minor item scores are on either side of M;
 - 3) When the 3 minor items score on one side of the memory score and the other 2 minor item scores on the other side of the memory score;
 - 4) When at least 3 minor items are 0, if $M=0.5$, then $CDR=0.5$;
 - 5) When only one minor item is ≥ 0.5 , if $M = 0$, $CDR = 0$.
4. $CDR \neq M$ (memory score)
 - 1) When 3 or more secondary item scores are greater or less than M, $CDR =$ most secondary item scores;
 - 2) When $M=0.5$, at least 3 minor items are ≥ 1 , $CDR=1$;
 - 3) When $M=0$, 2 or more minor items ≥ 0.5 , $CDR=0.5$;
 - 4) When $M \geq 1$, $CDR \neq 0$, at this time if most other minor items = 0, $CDR = 0.5$.
5. The principle of proximity: when the above principles are not met, the score of the closest secondary item of $CDR=M$ (eg: M and the score of a secondary item = 3, the score of 2 secondary items = 2, 2 The score of the secondary item is 1, $CDR = 2$).

CDR domain total score (sum of boxes)

Refers to the arithmetic sum of the scores of all six functional domains.

CDR supplement

According to the test situation, it is not included in the total score.

	Impairment				
	None 0	Questionable 0.5	Mild 1	Moderate 2	Severe 3
Memory	No memory loss or inconsistent forgetfulness	Consistent slight forgetfulness; partial recollection of events; "benign" forgetfulness	Moderate memory loss; more marked for recent events; defect interferes with everyday activities	Severe memory loss; only highly learned material retained; new material rapidly lost	Severe memory only fragments remain
Orientation	Fully oriented	Fully oriented except for slight difficulty with time relationships	Moderate difficulty with time relationships; oriented for place at examination; may have geographic disorientation elsewhere	Severe difficulty with time relationships; usually disoriented to time, often to place	Oriented to person only

Judgment & Problem Solving	Solves everyday problems & handles business & financial affairs well; judgment good in relation to past performance	Slight impairment in solving problems, similarities, and differences	Moderate difficulty in handling problems, similarities, and differences; social judgment usually maintained	Severely impaired in handling problems, similarities, and differences; social judgment usually impaired	Unable to make judgments or solve problems
Community Affairs	Independent function at usual level in job, shopping, volunteer and social groups	Slight impairment in these activities	Unable to function independently at these activities although may still be engaged in some; appears normal to casual inspection	No pretense of independent function outside home Appears well enough to be taken to functions outside a family home	Appears too ill to be taken to functions outside a family home
Home and Hobbies	Life at home, hobbies, and intellectual interests well maintained	Life at home, hobbies, and intellectual interests slightly impaired	Mild but definite impairment of function at home; more difficult chores abandoned; more complicated hobbies and interests abandoned	Only simple chores preserved; very restricted interests, poorly maintained	No significant function in home
Personal Care	Fully capable of self-care		Needs prompting	Requires assistance in dressing, hygiene, keeping of personal effects	Requires much help with personal care; frequent incontinence
_____ CDR sum of boxes					
_____ global CDR					

Score only as decline from previous usual level due to cognitive loss, not impairment due to other factors.

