7.2.14 Clinical Dementia Rating (CDR) [61] (Appendix 15)

The CDR is a refinement of information that the doctor obtains through conversations with the patient and his/her family, and to assess the degree of impairment of the patient's cognitive function, and then to quickly assess the severity of the patient's condition. The assessment of cognitive domains consists of six items: memory, orientation, judgment and problem solving, work and social ability, family life and hobbies, and independent living ability. The judgment is in five levels, "normal CDR=0, suspected dementia CDR=0.5, mild dementia CDR=1, moderate dementia CDR=2, severe dementia CDR = 3". The CDR-SOB (CDR sum of box) total score is a simple sum of the scores of the six items. CDR sum of boxes adds up the 6 items, and the total score ranges from 0 to 18. As long as the score is greater than 0, the subject has at least one cognitive impairment. Generally, the change value of CDR sum of boxes can be used in clinical trials to obtain more accurate cognitive evaluation[62]. CDR is a widely used measure of the severity of dementia.

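### Appendix 15's global CDR rules overlap with no stated precedence, so the same box scores can give two different global scores

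*Protocol*

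**What the plan says.** Protocol Appendix 15, under Global CDR, makes memory (M) the main item and the other five boxes secondary, then lists rules.

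Section 3, where the global CDR equals M:
- 3(1): "When at least 3 secondary items are the same as the memory score".
- 3(3): "When the 3 minor items score on one side of the memory score and the other 2 minor item scores" fall on the opposite side.
- 3(4): "When at least 3 minor items are 0" and M = 0.5, the result is 0.5.
- 3(5): "When only one minor item is" at 0.5 or above and M = 0, the result is 0.

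Section 4, where the global CDR differs from M:
- 4(1): "When 3 or more secondary item scores are greater or less than M", the result is the score held by most secondary boxes.
- 4(2): M = 0.5 and at least three secondary boxes at 1 or above, the result is 1.
- 4(3): M = 0 and "2 or more minor items" at 0.5 or above, the result is 0.5.
- 4(4): M of 1 or more excludes a global score of 0; if most secondary boxes are 0, the result is 0.5.

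Rule 2 limits the result to 0.5 or 1 when M = 0.5. Rule 5, a nearest-score principle, applies when the earlier rules are not met. That is the only statement about order. Section 7.2.14 labels global CDR 0 as normal, 0.5 as suspected dementia and 1 as mild dementia.

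**The concern.** A scoring algorithm should return one value for each set of inputs. Here several rules can be triggered by one set of boxes and return different values, and the text gives the rater no way to choose. This is not detail that a protocol may leave to the SAP: the algorithm is stated, and stated inconsistently.

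Section 2.1 promises data collected to a unified standard, and Section 10.2 asks for unified scoring and interpretation of the neuropsychological tests. The network has 68 centres (Section 2.2) and a research period to January 2038 or longer (Section 2.3). Two raters who both follow Appendix 15 could record different global scores for identical boxes. One participant's global score could also change between visits with no change in any box. Any analysis that groups or tracks participants by global CDR would carry that noise.

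**Working it through.** **Inputs.** The rules above, from Appendix 15. Memory and four secondary boxes take 0, 0.5, 1, 2 or 3. Personal care takes 0, 1, 2 or 3, because its 0.5 cell in the Appendix 15 table is empty. The plan gives no figure to reproduce.

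**Worked profiles**
- M = 0; secondary 0, 0, 0, 0.5, 0.5. Three boxes equal M, so 3(1) gives 0. Two boxes are at least 0.5, so 4(3) gives 0.5.
- M = 0.5; secondary 1, 1, 1, 0, 0. Three boxes above M and two below, so 3(3) gives 0.5. Rules 4(1) and 4(2) both give 1.
- M = 1; secondary 0.5, 0.5, 0.5, 2, 2. Three boxes below M and two above, so 3(3) gives 1. Rule 4(1) gives 0.5.

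**Counting convention.** A profile conflicts if no single value satisfies every rule it triggers. For 4(1), the score of most boxes is taken as the most frequent secondary score. Tied scores are all allowed, and values barred by rule 2 or 4(4) are removed first.

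**Boxes up to 1.** Profiles: 3 (memory) × 3⁴ (four secondary boxes) × 2 (personal care) = 486.
- 3(1) against 4(3): M = 0 with exactly two impaired secondary boxes. Both among the four ordinary boxes: C(4,2) × 2² = 24. One of them personal care: 4 × 2 × 1 = 8. Total 32, which is every such profile.
- 3(3) against 4(1) and 4(2): M = 0.5, three boxes at 1 and two at 0. C(5,3) = 10.
- 4(1) against 4(3): M = 0, at least three boxes impaired, and 0.5 not among the most frequent scores.
  - Score 1 alone most frequent: five 1s (1 profile), four 1s (9), three 1s (32), total 42.
  - Scores 0 and 1 tied at two boxes each with one box at 0.5: 12 + 12 = 24.
  - Total 66.

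Sum: 32 + 10 + 66 = 108 of 486 (22%). If 4(1) is held not to apply to ties, it is 108 − 24 = 84 (17%). If 4(1) yields to every other rule, it is 32 + 10 = 42 (9%).

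**Full range.** Profiles: 5 × 5⁴ × 4 = 12,500. Enumeration gives 3,060 conflicts (24%). With 4(1) yielding to the others:
- 3(1) against 4(3): C(4,2) × 4² + 4 × 4 × 3 = 96 + 48 = 144, again every M = 0 profile with exactly two impaired secondary boxes.
- 3(3) against 4(2): C(5,3) × 3³ = 270.
- 3(3) against 4(4): three boxes at 0 and two above M. For M = 1, 10 × 2² = 40; for M = 2, 10 × 1 = 10. Total 50.

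Sum: 144 + 270 + 50 = 464 of 12,500 (3.7%).

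The full-range total also depends on convention. Keeping the barred values and ignoring ties gives 3,530.

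**The case against.** The best defence is that the clashes mostly set a general rule against one tied to a particular memory score, and that a trained rater lets the specific rule win. That settles the first two worked profiles. The third sets two general rules, 3(3) and 4(1), against each other; it resolves only if the exact three-two split is also read as an exception. Appendix 15 calls its rules principles and asks for judgment, and Section 10.2 provides central rater training. These points lower the practical risk. They do not remove the problem, because none of this order is written down.

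The count is also open to challenge. Of the 108 conflicts, 66 come from 4(1) against 4(3), where 4(3) is plainly the specific rule. That is why the 42 and 464 are given beside the larger figures. All are unweighted combinations, and the M = 0 cases need intact memory with two or more other domains impaired.

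Two stronger readings are tempting, and the document does not support either.
- A reader might infer that CDR 0 versus 0.5 marks asymptomatic versus symptomatic, so that symptom onset is misdated. The protocol never defines symptomatic status by CDR. Section 6.2 items 8 to 10 diagnose dementia, AD and MCI by other criteria, the longitudinal model in Section 8 uses EYO and mutation status, and Section 6.6 sets visits by age at onset or confirmed decline. An effect on dating onset is only an inference.
- A reader might set Section 7.2.14's sentence on the sum of boxes, "As long as the score is greater than 0, the subject has at least one cognitive impairment", against rule 3(5). The two are compatible: a sum above 0 means that at least one box is non-zero, and a global score of 0 with one box at 0.5 is a different summary.

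**Conclusion.** The point holds as a defect in a stated scoring rule. Appendix 15 assigns two global CDR values to some box profiles, in places across the labels normal and suspected dementia or suspected and mild dementia.

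Its extent is 42 to 108 of 486 possible profiles with boxes up to 1, depending on how rule 4(1) is read, and 464 to 3,060 of 12,500 over the full range under the stated convention. Even on the charitable reading, every profile with M = 0 and exactly two impaired secondary boxes stays in conflict. The document does not say how many participants have such profiles, so the effect on real data is unknown. The CDR sum of boxes is not affected. The point should be corrected because the text is wrong as printed and the repair is cheap; no analysis named in Section 8 is shown to fail because of it.

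**What to change.** Reconcile sections 3 and 4 of the Global CDR rules by stating one explicit order of precedence, checked against the instrument's source scoring. The order cannot be derived from this document alone. It must return exactly one value for every profile, and two places are easily missed:
- M = 0 with all secondary boxes 0. Only rule 3(1) covers it; 3(5) needs one impaired box and 4(3) needs two. An order that keeps just those two for M = 0 leaves the fully normal profile unscored.
- Ties. Rule 5 has to stay. Appendix 15's own example (M = 3; secondary 3, 2, 2, 1, 1; result 2) ties at 2 and 1 under rule 4(1) and needs rule 5 to settle it.

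Then derive the global CDR centrally from the stored box scores and re-derive it for all past visits. The sum-of-boxes sentence in Section 7.2.14 needs no change.

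The cost is a wording change in the protocol and rater manual plus one derived variable in the database, with no new data collection. The downside is that some global scores already recorded may change; these should be listed.
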